- For patients who continue screening process, a diagnostic test using blood from the fingertip to detect IgG/IgM antibodies against the SARS-CoV-2 virus takes place (inclusion criterion 6). If the test is positive for any of IgM or IgG antibodies, screening stops. If the test for both IgG / IgM antibodies is negative, the patient may be included in the trial.

Sub-Study

Participants who will be included in the study in the Department of Clinical Therapeutics of the ALEXANDRA General Hospital of Athens, will participate in a sub-study at the Vascular Laboratory of the Therapeutic Clinic. The sub-study procedures are carried out within the framework of the planned visits of the patients and are analyzed in the paragraph "Patient visits and interventions".

Study visits (APPENDIX IV)

Visit 1 This visit is conducted immediately after the end of the screening procedure (month 0 of study) and involves the following:

- Recording of the following information: age and gender, pre-existing comorbidities, history of hospitalizations the last two years
- For the participants of the sub-study, the following procedures will be performed:
 - a) carotid and femoral artery ultrasound, b) heart ultrasound, and c) a blood sample of 10 ml (peripheral blood) will be collected for PBMC stimulation for cytokine production (see section "Sub-study procedures")
- Administration of placebo or BCG

Visit 2 This visit is conducted 45 ± 5 days from the date of visit 1. This visit may be done by phone call or through the internet. During this visit, the vaccinated subject is asked to provide answers to a specific questionnaire involving the incidence of respiratory tract infection (Appendix VI). All patients will also be asked for the incidence of cardiovascular events, such as any diagnosis of stroke, myocardial infarction or rupture of a abdominal aortic aneurysm.

Visit 3 This visit is conducted 90 ± 5 days from the date of visit 1. This is a visit conducted at the study site. During this visit, the following are done:

- IgG and IgM antibodies against SARS-CoV-2 are measured in the vaccinated subject in exactly the same method that was followed at the screening stage
- The vaccinated subject is asked to provide answers to a specific questionnaire involving the incidence of respiratory tract infection (Appendix VI). All patients will

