- Central blood pressure and reflected aortic waves: It will be evaluated using a special automated device (SphygmoCor System, AtCor Medical Pty Ltd, Sydney, Australia) in a non-bloody way on the carotid and femoral arteries.
- Endothelial function with ultrasound measurement of the dependent-from-the-endothelial dilation and mediated-from-the-nitrite dimension: It will be assessed using an ultrasound device and the measurement of the route-dependent vasodilator using a special 7-14 MHz audio recorder (Vivid 7 Pro, GE, USA) to be applied in a non-bloody way to the carotid and femoral arteries
- Carotid arteries intima-media thickness and Uterine Arteries: It will be evaluated using a B-mode ultrasound device and a special sound system (14.0 MHz multi-frequency linear array probe, Vivid 7 Pro, GE Healthcare, USA) in a non-bloody way on the carotid arteries. and femoral arteries.
- Cardiac ultrasound: The standard procedures of the clinical practice will be followed and the standard measurements will be taken using 2-D and Doppler ultrasound techniques.
- One blood sample will be taken from a forearm vein after antiseptic application and will be collected in tubes with anticoagulant agent. Isolation of PBMCs will be performed and they will be stimulated with purified bacterial antigens for cytokine production.

STUDY ENDPOINTS

Primary endpoint

The primary study endpoint is set on visit 3 (90 ± 5 days from the date of visit 1). The two groups of vaccination are compared for the primary endpoints which is composite. Patients who meet any of the following will be considered to meet the primary endpoint:

- Positive for the respiratory questionnaire endpoint when at least one of the following combination is met either at visit 2 and/or at visit 3 (see APPENDIX VI):
 - One situation definitively related to COVID-19

- All four questions of symptoms possibly related to COVID-19 answered YES
- At least two questions of symptoms possibly related to COVID-19 answered YES + need for admission at the emergency department of any hospital and/or need for intake of antibiotics answered YES
- At least four questions of symptoms probably related to COVID-19 answered YES one of which is “need for admission at the emergency department of any hospital and/or need for intake of antibiotics”
- Positive IgG or IgM antibodies against SARS-CoV-2

Secondary endpoints

The secondary endpoints are the difference between the two groups of vaccination in each of the following:

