The differences in the repeated measurements of the vascular parameters (arterial hardness, central arterial pressures, reflected waves, endothelial function and thickness of the inner-middle carotid sheath) will be estimated using randomly mixed models with two types: random effects (random intercept and random slope) and variance-covariance matrix. Vascular parameters will be used as dependent variables, after checking the normal distribution of their residuals with histograms and Q-Q plots graphs. In case of irregular distribution, appropriate transformations will be used (based on the neural index or using inverse ranking normalization).

INTERIM ANALYSIS

The Sponsor will appoint an independent committee to analyze the study and report the results of the primary endpoint once the last enrolled subject will reach visit 3. The study investigators will be informed on the results of the interim analysis but they will remain blind to the allocated arm of vaccination which will allow the study to end after the last visit of the last subject.

ADVERSE EVENTS

Adverse events (AEs) and Serious Adverse Events (SAEs) will be collected from baseline until the last patient's evaluation. Investigators should monitor subjects for adverse events and are responsible for recording ALL adverse events and serious adverse events occurring to a patient during the trial. Infection will not be reported as an SAE since this is the study primary endpoint.

An adverse event is any undesirable medical occurrence in a subject administered a pharmaceutical product and which does not necessarily have a causal relationship with this treatment. The time relationship is defined from the moment the AE occurs during therapeutic treatment until 30 days or 5 half-lives after treatment discontinuation. The adverse event may be a sign, a symptom, or an abnormal laboratory finding.

Serious adverse events (SAEs) must be reported to within 24 hours. If an adverse event meets any of the following criteria, it is considered SAE:

- **Death**
- **Life-threatening situation** The subject was at risk of death at the time of the adverse event/experience. It does not refer to the hypothetical risk of death if the AE were more severe or were to progress.
- **Inpatient hospitalization** or prolongation of existing hospitalization.

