Death* — no. (%)	8 (10.3)	5 (6.9)	0.57
SAEs with hospitalization* — no. (%)	20 (25.6)	10 (13.9)	0.10
Reason for hospitalization — no. (%)			
Arrhythmia	1 (1.3)	0 (0)	1.00
Stroke	2 (2.6)	1 (1.4)	1.00
Acute kidney injury	0 (0)	1 (1.4)	0.48
Deep vein thrombosis	1 (1.3)	0 (0)	1.00
Epilepsy	1 (1.3)	0 (0)	1.00
Electrolyte disturbance	1 (1.3)	0 (0)	1.00
Pulmonary edema	1 (1.3)	0 (0)	1.00
Anemia	1 (1.3)	0 (0)	1.00
ST-segment elevation at ECG	1 (1.3)	0 (0)	1.00
Elective surgery	2 (2.6)	2 (2.8)	1.00
SAEs without hospitalization — no. (%)			
Stroke — no. (%)	1 (1.3)	0 (0)	1.00
Syncope	0 (0)	1 (1.4)	0.48
Anemia	1 (1.3)	0 (0)	1.00

* - SAEs and deaths due to infections counting against the primary endpoint are not encountered here since per protocol they should not be reported as adverse events

Non-serious (AEs)

At least one non-serious AE — no. (%)	20 (25.6)	26 (36.1)	0.21
---------------------------------------	-----------	-----------	------

Type of non-serious AE — no. (%)

Varicella-zoster eruption	1 (1.3%)	0 (0)	1.00
Helicobacter pylori infection	3 (3.8)	0 (0)	0.24
Dacryocystitis	0 (0)	1 (1.4)	0.48
Hip fracture	2 (2.6)	0 (0)	0.49
Non-infection associated cough	4 (5.1)	11 (15.3)	0.06
Asymptomatic bacteriuria	2 (2.6)	7 (9.7)	0.09
Breast cancer	1 (1.3)	1 (1.4)	1.00
Renal cancer	0 (0)	1 (1.4)	0.48
Squamous skin carcinoma	0 (0)	1 (1.4)	0.48
Rash at the injection site	0 (0)	2 (2.8)	0.22
Otitis	0 (0)	1 (1.4)	0.48
Dental infection	2 (2.6)	1 (1.4)	1.00

References

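### The SAE exemption covers all infection, but the primary endpoint that justifies it is only respiratory/COVID-19 illness or SARS-CoV-2 antibodies up to visit 3

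*Protocol*

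**What the plan says.** The Adverse Events section of the protocol sets a general duty and then an exception.

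- Duty: investigators are responsible for "recording ALL adverse events and serious adverse events occurring to a patient during the trial". Adverse events and SAEs "will be collected from baseline until the last patient's evaluation"; the last scheduled visit is visit 5, at day 180.
- Exception, in the next sentence: "Infection will not be reported as an SAE since this is the study primary endpoint". It is not limited by type, severity, cause or timing of the infection.
- SAE criteria, in the same section: death, a life-threatening situation and inpatient hospitalisation are among them. The list makes no exception for infection. SAEs carry a 24-hour reporting duty.

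The Primary endpoint section defines a composite with two parts:

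- The questionnaire part is positive when "at least one of the following combination is met either at visit 2 and/or at visit 3".
- The serology part is "Positive IgG or IgM antibodies against SARS-CoV-2". Under Study visits, the post-vaccination antibody test is done at visit 3 (day 90).

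At each follow-up visit "the vaccinated subject is asked to provide answers to a specific questionnaire involving the incidence of respiratory tract infection".

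Appendix I describes the predecessor trial's version of the exemption, which covered adverse-event reporting as a whole, in the footnote to Table 6: "SAEs and deaths due to infections counting against the primary endpoint are not encountered here since per protocol they should not be reported".

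**The concern.** Exempting endpoint events from SAE reporting is defensible when the endpoint itself captures them, because each event is then counted once, in the efficacy data. That holds only if the exemption is no wider than the endpoint. Here it is wider. The predecessor's endpoint was any of a list of infections that included urinary, abdominal, soft-tissue and bloodstream infection, and its exemption was tied to those infections. This protocol narrows the endpoint to respiratory/COVID-19 illness and SARS-CoV-2 antibodies but words the exemption as infection without qualification.

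What is at stake is the safety comparison of a live vaccine in people aged 50 or over with comorbidity. An investigator who follows the sentence literally would not report a fatal bloodstream infection, or suspected infection by the vaccine strain, as an SAE. Neither is a primary endpoint event. Nothing else in the protocol is sure to catch such events: no mortality endpoint is listed, and the Interim Analysis section asks the independent committee to report the primary endpoint only.

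**Working it through.** The plan states no figure on this point, so the check sets the exemption beside the endpoint and the SAE criteria.

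| Event, when serious | Meets an SAE criterion? | Exempt as worded? | Assured capture in the primary endpoint? |
|---|---|---|---|
| Non-respiratory infection (urinary, abdominal, skin, bloodstream) | Yes | Yes | No. The questionnaire asks about respiratory symptoms, fever, emergency admission, antibiotics and a molecular COVID-19 diagnosis, not the type of infection |
| Infection by the vaccine strain | Yes | Yes, because infection is unqualified | No |
| Any infection after day 90 | Yes | Yes | No. The primary endpoint closes at visit 3; visits 4 and 5 repeat the questionnaire as secondary endpoints, without serology |
| Fatal COVID-19 not yet captured when the participant dies | Yes (death) | Yes | No. The questionnaire is put to the participant, the antibody sample comes from the participant at visit 3, and no proxy or record source is named |

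**Time.** SAE collection runs from day 0 to day 180 and the primary endpoint closes at day 90. The exemption therefore outlasts its stated reason for 180 − 90 = 90 days, which is 90/180 = 50% of nominal follow-up.

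**Indication from the predecessor (Appendix I).**

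- Deaths: the one-year mortality row of Table 3 gives 14 (placebo) + 10 (BCG) = 24. The adverse-event table (Table 6) gives 8 + 5 = 13. The difference is 24 − 13 = 11, that is 6 placebo and 5 BCG, or 11/24 = 46%. This agrees with the Table 6 footnote, though causes of death are not tabulated.
- Infection types in Table 3: respiratory 24 + 6 = 30. Non-respiratory, placebo: 3 + 6 + 6 + 2 = 17. Non-respiratory, BCG: 4 + 8 + 3 + 0 = 15. Non-respiratory share: 32/(30 + 32) = 32/62 = 52%.

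The 62 are table entries, not patients. Table 3 counts 33 + 18 = 51 patients with at least one infection and notes that some had more than one. Seriousness is not given. The patients were 65 or over, newly discharged from hospital, with a mean age near 80, and were followed for 12 months. These figures show that infections outside the new endpoint, and deaths left out of an adverse-event table, are not rare in that setting. They do not estimate the number in this trial.

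**The case against.** The strongest reply is that the sentence carries its own limit. It gives the primary endpoint as its reason, so a sensible investigator would apply it to endpoint infections only. The predecessor's footnote says exactly that, and its Table 6 still lists infections outside its endpoint, such as varicella-zoster, otitis and dental infection, among non-serious events. This reading is probably what was meant. It is not what the sentence says, and a 24-hour reporting rule should not depend on each site inferring a limit that the predecessor wrote out and this protocol leaves out.

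Several stronger readings are tempting, and the documents do not support them:

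- *That these events are recorded nowhere.* All adverse events must still be recorded; the exception concerns reporting as an SAE. The Table 6 footnote does show that a related rule was applied to adverse-event reporting as a whole, so the general duty is a weak safeguard, but it exists.
- *That the primary endpoint is purely self-reported.* Antibodies measured at the site are a stand-alone component, and non-fatal COVID-19 may be caught there.
- *That fatal cardiovascular events share the gap.* They are not infections, so no exemption applies and death remains an SAE criterion.
- *That the adverse-event window contradicts itself.* Collection to the last evaluation can coexist with a time relationship that runs "until 30 days or 5 half-lives after treatment discontinuation". One sets what is collected and the other defines a term that the causality categories use.
- *That the predecessor's 11 deaths measure a loss.* They were reported, in that trial's mortality row.
- *That the composite must be rebuilt to include death or hospitalisation.* That is a design trade-off. How deaths before visit 3 enter the analysis is commonly left to the SAP, which is not at hand.

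**Conclusion.** The point stands as a mismatch of scope that bears on safety reporting. The exemption covers all infection, while its stated reason covers only respiratory/COVID-19 illness reported at visits 2 and 3 and antibodies at visit 3. It also conflicts with the death, life-threatening and hospitalisation criteria in its own section. Four kinds of event are affected: serious non-respiratory infection, vaccine-strain infection, serious infection after day 90, and COVID-19 that is fatal before visit 2 or 3 can capture it. As written they are not reportable as SAEs and have no assured capture as endpoint events.

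The number of such events cannot be derived from the protocol, and no bias in the primary comparison is claimed. The conclusion rests on reading the exemption literally. Vaccine-strain infection falls under it only because the word infection is unqualified; the protocol does not name that event. If sites were instructed to apply the predecessor's narrower rule, most of the gap would close, but nothing in the protocol tells them to.

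**What to change.** Reconcile the exemption in the Adverse Events section with the Primary endpoint section and with the SAE criteria. Limit it to events actually recorded as meeting the primary endpoint, as the predecessor's rule was limited to infections that counted for its endpoint. State that every death, and every other serious infection including suspected vaccine-strain infection, stays under SAE reporting throughout follow-up. The composite endpoint need not change.

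Cost: a protocol amendment, a note to sites and slightly more SAE forms. Sample size, visits and the primary analysis are unaffected.

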APPENDIX I Interim analysis of the ACTIVATE trial

A RANDOMIZED CLINICAL TRIAL FOR ENHANCED TRAINED IMMUNE RESPONSES THROUGH BACILLUS CALMETTE-GUÉRIN VACCINATION TO PREVENT INFECTIONS OF THE ELDERLY: THE ACTIVATE TRIAL

INTERIM ANALYSIS

By the board of April 29th 2020

Participants:

[name] [name], chairing

[name] [name]

[name]

ACTIVATE was a prospective randomized open-label controlled trial among patients hospitalized at the 4th Department of Internal Medicine of ATTIKON University General Hospital in Greece. The protocol and its subsequent amendments were approved by the National Institutional Review Board and the National Ethics Committee of Greece, and by the Ethics Committees of ATTIKON hospital (EudraCT number, 2017-000596-87; ClinicalTrials.gov NCT03296423).

The study enrolled elderly patients (age \geq 65 years) of both genders who were discharged from hospital after hospitalization for a medical cause. The main exclusion criteria were: a) solid organ malignancy or lymphoma diagnosed the last five years; b) treatment with oral or intravenous steroids defined as daily doses of 10mg prednisone or equivalent for longer than 3 months; c) severe immunodeficiency like infection by the human immunodeficiency virus, neutropenia, transplantation, intake of chemotherapy, primary immunodeficiency, severe and treatment with anti-cytokine therapies; and d) positive Interferon-gamma Release Assay (IGRA). All patients or their legal representatives provided written informed consent before enrollment.

On the day of hospital discharge and after careful recording of detailed medical history and laboratory examinations for the inclusion and exclusion criteria, patients remaining eligible underwent IGRA test. Those who had negative IGRA were allowed to be enrolled in the study. Participants were randomized to one intradermal vaccination 0.1ml of sodium chloride 0.9% or with 0.1ml of BCG (BCG vaccine Bulgaria strain 1331; Intervax). Randomization was performed in a 1:1 ratio by a biostatistician and was kept in a sealed envelope, which was delivered to the investigators for treatment allocation at randomization.

The primary outcome was the time interval to the first infection post hospital discharge between the two groups of treatment. This was a composite endpoint involving any of the following infections: respiratory tract infections of probable viral origin necessitating medical attention; bacteremia; community-acquired pneumonia; hospital-acquired pneumonia; urinary tract infection; intraabdominal infection; and soft-tissue infection. The definitions of these infections are provided in the Supplementary Appendix.

Secondary study outcomes included the rate of hospitalizations until month 12; the time to first sepsis episode; the total number of infections; the time to first hospitalization; the number of antibiotic courses; and one-year mortality. Sepsis was

defined by the Sepsis-3 definitions, i.e., sequential organ failure assessment (SOFA) score of ≥ 2 points for emergency admission patients and a ≥ 2 -point increase on the admission SOFA score for hospitalized patients.

Patients' visits were conducted every month for 12 months. During each visit the following data were captured: history of any new infection; any new hospitalization followed by thorough study of hospital discharge notes and contact with treating physicians if necessary; any need for antimicrobial prescription; and patient disposition. All patients were monitored throughout the study period for adverse events and serious adverse events.

The sample size was calculated assuming the median time to new infection would be 4 months in the placebo group and 7 months with BCG vaccination. To achieve so with 90% power at the 5% level of significance, 100 patients were allocated to each arm. The interim analysis included only patients with completed 12-month of follow-up. In order to preserve the overall Type I error rate at 5 %, an adjustment of the level of significance of the interim and final analysis was done by O'Brien-Fleming strict alpha adjustment¹. This adjustment provides significance $\alpha=0.0054$ at interim and $\alpha=0.0492$ at final. Time-to-event comparisons were done by the log-rank test and Cox regression reporting the hazard ratio (HR) with 95% confidence intervals (CI); quantitative data were compared by the Fisher's exact test. and by forward step-wise logistic regression analysis. A sensitivity analysis was conducted to assess robustness, in which the entire number of participants (198) was entered. Analysis was conducted using IBM SPSS Statistics v. 26.0. All p-values were two-sided and any p-value <0.05 was considered as statistically significant. The complete statistical analysis plan is provided in the protocol.

RESULTS

Patients

From September 2017 through August 2019, 202 patients were enrolled and randomized; four patients withdrew consent and requested removal of all data, leaving a final intention-to-treat analysis cohort of 198 patients. No patient was reported as lost to follow-up (Figure 1). Interim analysis included 78 patients allocated to placebo vaccination and 72 patients allocated to BCG vaccination. Baseline characteristics were similar between the two arms (Tables 1 and 2).

Primary and secondary outcomes

The primary outcome of the time until a new infection was significantly prolonged in the placebo vaccination group compared to the BCG vaccination group ($P=0.04$) (Figure 2). The hazard ratio of 0.53 provides indication that the rate of infection was almost twofold in the placebo group in comparison to the BCG group. The incidence of new infection was 37.2% (95% CIs 27.3-48.3%) in the placebo group and 20.8% (95% CIs 13.0-35.6%) in the BCG group with an odds ratio of 0.44 (Table 3). It is interesting to note that the main differences between the two groups involved infections of the respiratory system (Respiratory or viral infection necessitating medical treatment, community-acquired pneumonia and hospital-acquired pneumonia), where the odds ratio is reduced to 0.20 (Table 3 and Figure 3).

Stepwise logistic regression analysis showed that BCG vaccination was an independent protective factor from the incidence of new infection until month 12 (odds ratio, 0.44; 95% CI, 0.21 to 0.94; $P=0.03$) (Table 4). Sensitivity analysis including the total sample confirmed the findings (Table 5).

Major benefit from BCG vaccination was observed in one main secondary endpoint: mean number of infections until month 12 being 0.44 in the placebo group and 0.25 in the BCG group ($P= 0.03$) (Table 3). No difference in the other secondary endpoints was found between the two groups (Table 3).

A trend for lower serious adverse event was recorded in the BCG vaccination group than in the placebo group (Table 6). Moreover, the incidence of non-serious adverse events did not differ between the two groups. None of the adverse events were related to the study.

A RANDOMIZED CLINICAL TRIAL FOR ENHANCED TRAINED IMMUNE RESPONSES THROUGH BACILLUS CALMETTE-GUÉRIN VACCINATION TO PREVENT INFECTIONS BY COVID-19: THE ACTIVATED II TRIAL

[figure not shown]

Figure 1. Screening, Randomization, and Follow-up.

Abbreviations: BCG: Bacillus Calmette-Guérin; HIV human immunodeficiency virus; IGRA: interferon-gamma releasing assay

[figure not shown]
[figure not shown]

Figure 2. Cumulative Incidence of the Event of First Infection in the Two Groups of Vaccination

Infections counting against the primary endpoint were respiratory infection of probable viral origin necessitating medical attention, community-acquired pneumonia, hospital-acquired pneumonia, intraabdominal infections, urinary tract infection, bloodstream infections and acute bacterial skin and skin structure infections

% difference with 95% CI of events between placebo and BCG

Figure 3 % difference of the incidence of each infection and 95% confidence intervals between the two groups

Table 1. Baseline Characteristics of Enrolled Patients.

	Placebo (N=78)	BCG (N=72)	p-value
Age (years), mean (SD)	79.6 (7.8)	79.9 (7.6)	0.80
Male gender — no. (%)	35 (44.9)	32 (44.4)	1.00
CCI, mean (SD)	5.5 (1.9)	5.5 (2.2)	0.91
APACHE II score on hospital discharge, mean (SD)	7.9 (3.0)	8.1 (2.9)	0.70
SOFA score on hospital discharge, mean (SD)	1.2 (1.4)	1.0 (1.1)	0.59
Comorbidities (%)			
Diabetes mellitus — no. (%)	29 (37.2)	23 (31.9)	0.61
without organ damage — no. (%)	23 (29.5)	15 (20.9)	0.26
with organ damage — no. (%)	6 (7.7)	8 (11.1)	0.58
Chronic heart failure — no. (%)	23 (29.5)	20 (27.8)	0.86
Chronic renal disease — no. (%)	14 (17.9)	12 (16.7)	1.00
Chronic obstructive pulmonary disease — no. (%)	12 (15.4)	11 (15.3)	1.00
Cerebrovascular disease — no. (%)	17 (21.8)	21 (29.2)	0.35
Degenerative disease — no. (%)	8 (10.3)	6 (8.3)	0.78
Myocardial infarct — no. (%)	13 (16.7)	9 (12.5)	0.49
Biliary stones — no. (%)	10 (12.8)	11 (15.3)	0.81
Renal stones — no. (%)	1 (1.3)	1 (1.4)	1.00
Any surgery — no. (%)	30 (38.5)	30 (41.7)	0.74
Dementia — no. (%)	15 (19.2)	20 (27.8)	0.25
Hemiplegia — no. (%)	1 (1.3)	1 (1.4)	1.00
Peptic ulcer disease — no. (%)	3 (3.8)	3 (4.2)	1.00
Peripheral vascular disease — no. (%)	1 (1.3)	0 (0)	1.00

Liver disease — no. (%)	1 (1.3)	1 (1.4)	1.00
Hypertension — no. (%)	56 (71.8)	53 (73.6)	0.86
Atrial fibrillation — no. (%)	30 (38.5)	22 (30.6)	0.39

Abbreviations: APACHE Acute physiology and chronic health evaluation; CCI: Charlson’s Comorbidity Index; SD standard deviation; SOFA sequential organ failure assessment.

Table 2. Causes of hospital admission before study enrolment

Cause of hospital admission	Placebo (N=78)	BCG (N=72)	p-value
Lower respiratory tract infection — no. (%)	20 (25.6)	23 (31.9)	0.47
Biliary tract infection — no. (%)	8 (10.3)	7 (9.7)	1.00
Ischemic stroke — no. (%)	10 (12.8)	12 (16.7)	0.65
Acute kidney injury — no. (%)	4 (5.1)	4 (5.6)	1.00
Gastrointestinal tract bleeding — no. (%)	8 (10.3)	6 (8.3)	0.78
Anemia — no. (%)	4 (5.1)	2 (2.8)	0.68
Electrolyte disturbance — no. (%)	2 (2.5)	4 (5.6)	0.43
Pulmonary embolism — no. (%)	2 (2.6)	2 (2.8)	1.00
Cerebral hemorrhage — no. (%)	1 (1.3)	1 (1.4)	1.00
Acute pyelonephritis — no. (%)	6 (7.7)	2 (2.8)	0.28
ABSSI — no. (%)	4 (5.1)	0 (0)	0.12
Other disease — no. (%)	9 (11.5)	8 (11.1)	1.00

Abbreviation: ABSSSI: acute bacterial skin and skin structure infection

Table 3. Primary and Secondary Study Outcomes.

	Placebo (N=78)	BCG (N=72)	Odds Ratio (95% CI)	p-value
Patients with at least one new infection until month 12 — no. (%)*	33 (42.3)	18 (25.0)	0.46 (0.23-0.91)	0.04
Respiratory or viral infection necessitating medical treatment— no. (%)	14 (17.9)	3 (4.2)	0.20 (0.06-0.72)	0.01
Community-acquired pneumonia — no. (%)	8 (10.3)	3 (4.2)	0.38 (0.10-1.49)	0.21
Hospital-acquired pneumonia — no. (%)	2 (2.6)	0 (0)	-	0.50
Total respiratory infections — no. (%)	24 (30.1)	6 (8.3)	0.20 (0.08-0.54)	0.00
Intrabdominal infection — no. (%)	3 (3.8)	4 (5.6)	1.47 (0.32-6.81)	0.71
Urinary tract infection — no. (%)	6 (7.7)	8 (11.1)	1.5 (0.49-4.56)	0.58
Acute bacterial skin and skin structure infection — no. (%)	6 (7.7)	3 (4.2)	0.52 (0.13-2.17)	0.50
Bloodstream infection — no. (%)	2 (2.6)	0 (0)	-	0.49
Mean rate of hospitalization/patient until month 12 (SD)	0.49 (0.72)	0.43 (0.72)	N/A	0.63
Mean number of infections until month 12 (SD)	0.44 (0.61)	0.25 (0.52)	N/A	0.03
Mean courses of antibiotics until month 12 (SD)	0.69 (1.66)	0.60 (1.25)	N/A	0.44

One-year mortality — no. (%)	14 (17.9)	10 (13.9)	0.74 (0.31-1.78)	0.51
------------------------------	-----------	-----------	------------------	-------------

*some patients had more than one infection

Abbreviations: CI confidence interval; N/A not applicable; SD; standard deviation. * - differences in proportion with 95% CI, shown as percentages.

Table 4. Univariate and multivariate analysis of the effects of covariates on the incidence of at least one infection until month 12

Covariates	Univariate analysis			Multivariate analysis		
	OR	95% CI	p-value	OR	95% CI	p-value
Group of vaccination	0.46	0.23-0.91	0.03	0.43	0.21-0.88	0.02
Myocardial infarct	2.71	1.08-6.79	0.03	-	-	0.06
COPD	3.0	1.21-7.46	0.02	3.14	1.24-7.95	0.02

* Covariates that failed to enter the stepwise logistic regression model

Table 5. Sensitivity analysis of the incidence of new infections

	Placebo n/ total (%)	BCG n/total (%)	Difference			
			in proportion		OR	95% CI
			% (95% CI)			
Interim (150)	33/78 (42.3)	18/72 (25.0)	17.3 (2.1-31.3)	0.46	0.23-0.91	0.04
Total (198)	41/98 (41.8)	27/100 (27.0)	14.8 (1.6-27.4)	0.51	0.28-0.93	0.04

Abbreviations: CI: confidence interval; OR: odds ratio

Table 6. Adverse Events (AEs)

Serious AEs	Placebo (N=78)	BCG (N=72)	p-value
Presence of at least one SAE* — no. (%)	30 (38.5)	17 (23.6)	0.05
Death* — no. (%)	8 (10.3)	5 (6.9)	0.57
SAEs with hospitalization* — no. (%)	20 (25.6)	10 (13.9)	0.10
Reason for hospitalization — no. (%)			
Arrhythmia	1 (1.3)	0 (0)	1.00
Stroke	2 (2.6)	1 (1.4)	1.00
Acute kidney injury	0 (0)	1 (1.4)	0.48
Deep vein thrombosis	1 (1.3)	0 (0)	1.00
Epilepsy	1 (1.3)	0 (0)	1.00
Electrolyte disturbance	1 (1.3)	0 (0)	1.00
Pulmonary edema	1 (1.3)	0 (0)	1.00
Anemia	1 (1.3)	0 (0)	1.00
ST-segment elevation at ECG	1 (1.3)	0 (0)	1.00
Elective surgery	2 (2.6)	2 (2.8)	1.00
SAEs without hospitalization — no. (%)			
Stroke — no. (%)	1 (1.3)	0 (0)	1.00
Syncope	0 (0)	1 (1.4)	0.48
Anemia	1 (1.3)	0 (0)	1.00

* - SAEs and deaths due to infections counting against the primary endpoint are not encountered here since per protocol they should not be reported as adverse events

Non-serious (AEs)

At least one non-serious AE — no. (%)	20 (25.6)	26 (36.1)	0.21
---------------------------------------	-----------	-----------	------

Type of non-serious AE — no. (%)

Varicella-zoster eruption	1 (1.3%)	0 (0)	1.00
Helicobacter pylori infection	3 (3.8)	0 (0)	0.24
Dacryocystitis	0 (0)	1 (1.4)	0.48
Hip fracture	2 (2.6)	0 (0)	0.49
Non-infection associated cough	4 (5.1)	11 (15.3)	0.06
Asymptomatic bacteriuria	2 (2.6)	7 (9.7)	0.09
Breast cancer	1 (1.3)	1 (1.4)	1.00
Renal cancer	0 (0)	1 (1.4)	0.48
Squamous skin carcinoma	0 (0)	1 (1.4)	0.48
Rash at the injection site	0 (0)	2 (2.8)	0.22
Otitis	0 (0)	1 (1.4)	0.48
Dental infection	2 (2.6)	1 (1.4)	1.00

References

